1. **Protocol Title:** impact of Virtual Reality on pre-procedural anxiety prior to Heart cathEterizAtion – VR-THEIA
2. **Investigators:** [name]; [name], MEd; [name], MSN
3. **Version Date:** 19 August, 2021
4. **Objectives:**

The primary aim of this study is to test the hypothesis that use of VR combined with standard procedural education will result in less pre-procedural anxiety than standard procedural education alone among patients undergoing first-time cardiac catheterization. The VR technology being evaluated in this study will allow patients to experience a 3-D simulation of certain aspects of their upcoming procedure prior to the actual procedure date.
5. **Background:**

It has been reported that patients scheduled for cardiac catheterization experience considerable anxiety in anticipation of undergoing the procedure (1-3). This pre-procedural anxiety has the potential to adversely impact quality of life and could reduce overall patient satisfaction.

Virtual reality (VR) is the computer-generated simulation of a three-dimensional (3-D) environment that can be interacted with in a seemingly real, or physical, manner (4). VR technology, although previously expensive to produce and use, is becoming more affordable. When introduced into contemporary medical care, VR has the potential to alter the medical landscape and could be used in novel ways to improve patient satisfaction and clinical outcomes. The proposed study is being performed to determine if VR can be applied to reduce pre-procedural anxiety prior to cardiac catheterization.
6. **Setting of the Research:**

The research activities will be conducted at or from Spectrum Health outpatient offices and the Meijer Heart Center whenever possible. Potential participants will be called on the phone to discuss participation; if they agree to proceed, they will be met in person at an outpatient Spectrum Health facility, unless otherwise requested by the potential participant (e.g., if the would-be participant requests we meet her or him at an office or other public location and is comfortable conducting study activities in that locale, we would grant that request out of consideration for that participant's wishes) for signing of consent and baseline activities. Study personnel will then meet the participant on the day of her or his procedure in the Meijer Heart Center Catheterization Lab to conduct the preprocedure activities.
7. **Resources Available to Conduct this Research:**

Members of the Cardiovascular Research team will be available to conduct this study. In fiscal year 2015-2016, 3,800 left heart catheterizations (LHC) were performed at the Meijer Heart Center. Approximately 35% of those procedures were first time LHC's for the patient which equates to approximately 26 patients per week. If a minimum of 2 patients per week agreed to participate, the study team could enroll the target number of 172 participants (who successfully completed all study activities) and conclude all study activities in two years. Approximately 1% of the PI's time and 10% of each coordinator's/assistant's time will be devoted to the conduct of this study. The aggregate research experience of the team, including the PI, is over 20 years and includes prospective, retrospective, randomized, industry sponsored, federally funded and investigator initiated studies.

The current team has enrolled over 250 participants in studies over the past two years and successfully followed participants, collected and reported data and contributed to multiple publications.

The members of the team conducting this study are a subspecialty group within the Cardiovascular Research (CVR) Department. The CVR Department is comprised of five subspecialty teams totaling an average of 20 coordinators/nurses/assistants. The teams report to a cardiovascular research supervisor and the CVR Department is a subset of the Office of Research Operations at Spectrum Health. Our offices include individual works stations each (with computers connected to the SH servers and hospital software applications) for all staff, two conference rooms, a lab room, separate secure storage rooms, hoteling for monitors, a private office for leadership, high density storage and a full time secretarial administrator.

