## **8. Study Design:**

### **a. Recruitment Methods**

Patients scheduled for outpatient LHC will be screened for inclusion/exclusion criteria via the catheterization laboratory schedule. Upon review of those medical records, patients who appear to meet all inclusion criteria and have no exclusion criteria and whose procedure date allows for a baseline visit preprocedure will be called by study personnel to discuss study participation. Whenever possible, a PDF of the consent form will be sent to the patient directly (e.g. via email or fax). If the immediate transmission of a consent form is not technologically possible, study personnel will verbally present all elements of the study. If the patient chooses to proceed with participation, a date and time will be agreed upon to meet at an agreed upon location (Spectrum Health facility whenever amenable). At that visit, study personnel will again review all elements of the consent form, procure written consent and then proceed with baseline activities. A one-time gift card valued at \$25.00 will be provided to the participant at the conclusion of the visit. The total number of participants to be enrolled in this study will be up to 200.

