**Visit 1 - Baseline.** All participants will be required to meet with study personnel at an offsite locale (Spectrum Health facility whenever possible) prior to the scheduled LHC to conduct the baseline visit. Once informed consent is obtained, study personnel will administer the State Trait Anxiety Inventory (STAI) assessment to all participants.

**Randomization.** Following the completion of the STAI assessment, participants will be randomized in a 1:1 fashion to undergo either VR combined with standard procedural education or to standard procedural education alone. Prior to enrollment of the first participant, Spectrum Health Office of Research Administration statisticians (who are not be study personnel) provided the randomization assignment schema to Cardiovascular Research staff (also not study personnel). Each assignment was placed in an envelope in the order designated by the statisticians' assignment schema. The envelopes were sealed and sequentially numbered from "1" to "200". The envelopes were stored in the research office in the high-density storage area.

Due to the COVID-19 Pandemic, study personnel are now working primarily from home.

In order to maintain the randomization schema as designed as well as reduce the need for staff to go into the hospital to collect randomization envelopes (thereby reducing their risk of exposure), the randomization process will be, for the remainder of the study, via REDCap database. The coordinator attending the enrollment visit will use REDCap to learn the randomization assignment for that participant while in the field, thus maintaining the blind.

For participants randomized to standard procedure education alone, the baseline visit will be complete. Participants will be thanked (and provided a gift card) and remaining study activities will be reviewed.

For participants randomized to VR intervention, the following will occur:

- A baseline wellness self-assessment will be administered (reporting on absence or presence and degree of severity of headache, nausea, dizziness, fatigue and vision abnormalities)
- The participant will be asked to confirm she or he is seated comfortably and study personnel will ensure the chair and participant are free of direct obstruction

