### ***Visit 2 – Procedure Day***

Study personnel will meet participants in their Prep/Recovery room prior to their procedure and the STAI assessment will be administered to all. A Retrospective Wellness questionnaire will be administered to the VR intervention group only in order to assess for any longer-term adverse effects (e.g., headache lasting several hours) of the VR experience. Postprocedure, a patient preparedness survey will be administered to all participants. All participants will again be thanked for their participation, all questions will be answered and their study participation will conclude.

All of the above activities except for standard procedural education will be research related. The average study participation time frame for all participants will be less than 1 month.

The data collected for this study entails the State-Trait Anxiety Inventory results, wellness self-assessments results, preparedness survey results and meta-data results.

e. Data Management

The data collected for this study will comprise of survey results (State-Trait Anxiety Assessment; VR related wellness assessments; and a preparedness assessment) as well as demographic and medical history data (for general reporting purposes). The data will be collected directly from participants using paper tools, where after the responses will be entered into an electronic data capture (EDC) system. The study EDC will be housed on secure Spectrum Health servers and the paper documents will be stored in secure Spectrum Health facilities.

f. Withdrawal of Subjects

Participants may change their minds at any time and choose to withdraw from this study; however, there are no circumstances under which participants would be withdrawn without their consent.

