## 9. Statistical Plan

a. Sample Size Determination

Using G\*Power 3.1.5 and looking at two sample independent t-test for the primary endpoint, in order to detect an effect size of 0.5 between the groups at 90% power and using significance level of 0.05, 86 patients are required in each study group.

b. Statistical Methods

Categorical variables will be reported as count (frequency). Normally distributed continuous variables will be reported as mean  $\pm$  standard deviation and non-normally distributed continuous variables will be reported as median (interquartile range). To determine if there is a difference in the two groups demographic variables a two sample t-test will be used for normally distributed continuous variables, a Mann Whitney Test will be used for non-normally distributed continuous variables, and a Chi-square will be used for categorical variables unless assumptions aren't met then Fishers Exact test will be used. To compare the anxiety levels of the group of individuals randomized to VR and standard procedural education vs. standard procedural education alone an independent two sample t-test will be used. If assumptions aren't met then a Mann Whitney test will be used. To determine if there is a difference in anxiety before and after the use of VR a paired t-test will be used. If assumptions aren't met then a Wilcoxon Signed Rank test will be used. Significance will be assessed at an alpha of 0.05.

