## 10. Risks to Subjects

Possible documented risks to using virtual reality include seizures; loss of awareness; eye strain; eye or muscle twitching; involuntary movements; altered, blurred, or double vision or other visual abnormalities; dizziness; disorientation; impaired balance; impaired hand-eye coordination; excessive sweating; increased salivation; nausea; lightheadedness; discomfort or pain in the head or eyes; drowsiness; fatigue; and/or motion sickness.

About 1 in 4000 may have severe dizziness, seizures, eye or muscle twitching or blackouts triggered by light flashes or patterns, and this may occur while they are watching TV, playing video games or experiencing virtual reality, even if they have never had a seizure or blackout before or have no history of seizures or epilepsy. Such seizures are more common

in children and young people under the age of 20. These risks are generally associated with prolonged use and with the complete VR systems which entail large, fitted headsets and full body utilization. The VR hardware being used for this study is a reductive version (a hand-held View-Master with a smartphone), the participants will be seated for the duration and the experiences will last 10-15 minutes. The participant will be in complete control and can set down the View-Master at any time as well as choose to discontinue the experience.

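### Does counting the target of 172 as full completers mean that the analysed groups are not the randomized groups?

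*Combined protocol and SAP*

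**What the plan says.** The completion condition appears once, in section 7 (Resources Available to Conduct this Research), which gives "the target number of 172 participants (who successfully completed all study activities" as the number the team could enrol in two years. Section 8a sets the ceiling: "The total number of participants to be enrolled in this study will be up to 200".

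Section 9a derives the sample size "in order to detect an effect size of 0.5 between the groups at 90% power and using significance level of 0.05" and concludes that "86 patients are required in each study group". It attaches no completion condition. Section 9b then compares anxiety by a two-sample t-test (Mann-Whitney if assumptions fail) and identifies each group by the arm to which its members were randomized. Section 8c names the primary outcome as anxiety just before catheterization, compared between the two study groups.

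Under Randomization in section 8d, "participants will be randomized in a 1:1 fashion" once the baseline STAI is done. The control baseline visit then ends. The VR arm goes on to a wellness form, the VR session and a second wellness form, with a third on the procedure day. Section 10 says that the participant "can set down the View-Master at any time as well as choose to discontinue the experience". For both arms, "Postprocedure, a patient preparedness survey will be administered to all participants".

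The documents do not define the analysis population, give a missing-data rule or say what counts as successful completion.

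**The concern.** The 172 is exactly 2 x 86, so the one sentence that says who counts towards the powered number appears to count only people who did everything. Everything is not the same in the two arms. The VR arm has extra steps, one of which can be stopped at will, and VR can cause nausea and dizziness. The preparedness survey comes after the primary outcome, so someone with a valid procedure-day STAI could fail to count for lack of a later form.

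If the analysis kept only completers, the comparison would be conditioned on events after randomization that differ by arm. If those who stop the VR are the more anxious patients, removing them lowers the VR mean and produces an apparent benefit where none exists. Participants know their arm and no analysis set is named, so the choice might also be made after the data are seen.

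**Working it through.** **1. The plan's own figure.** Inputs from section 9a: standardized difference 0.5, power 90%, alpha 0.05, two equal groups. Sidedness is not stated, so two-sided is tried first.

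- Normal approximation: n = 2(1.960 + 1.282)² / 0.5² = 2 x 10.51 / 0.25 = 84.1, rounded up to 85.
- Noncentral t, two-sided: n = 85.03, rounded up to **86**. Power at 86 is 90.3%.
- One-sided versions give 69 (normal) and 70 (t), so the plan's figure is two-sided.

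The 86 is correct, and 2 x 86 = 172.

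**2. What the section 7 sentence is for.** It sits among volume and staffing figures: 3,800 x 0.35 / 52 = 25.6 first-time procedures a week, given as about 26; two consenting patients a week over two years is 2 x 104 = 208, enough to reach the cap of 200. Against that cap, 172/200 = 86%, which leaves 14% for attrition. The parenthesis explains why up to 200 are enrolled to obtain 172. It qualifies the total, not the 86 in each group.

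**3. Activities by arm, from section 8d.**

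| Activity | Control | VR |
|---|---|---|
| Baseline STAI (before randomization) | yes | yes |
| Wellness form before VR | no | yes |
| VR session | no | yes |
| Wellness form after VR | no | yes |
| Procedure-day STAI (primary outcome) | yes | yes |
| Retrospective wellness form | no | yes |
| Preparedness survey | yes | yes |
| Total | 3 | 7 |

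The asymmetry is real. It does not follow that an early stopper fails to complete. Section 8d sets no minimum exposure: the session ends when the participant says so, and the second wellness form follows. The freedom described in section 10 concerns the headset, not study membership. Section 8f lets participants in either arm withdraw and says that nobody is withdrawn without their own consent. No replacement procedure is described.

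**4. Power, if completers were nevertheless used.** With 100 randomized per arm and 172 completers in total:

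- 86/86: 90.3%
- 95/77 (5% and 23% lost): 90.0%
- 100/72 (0% and 28% lost): 89.6%

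Power hardly moves. If all 200 supply the procedure-day STAI, it is 94.0%.

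**5. Bias, if completers were nevertheless used.** Let v be the fraction of the VR arm excluded and g the excess STAI of those excluded over those kept, in SD. The full VR mean equals the completer mean plus v x g, so with no true effect and no control losses the completer contrast is shifted towards VR by v x g. Neither v nor g is in the documents. The rejection rates take 100 controls and 100(1 - v) VR participants.

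| v | g | Shift (SD) | Two-sided rejection |
|---|---|---|---|
| 5% | 0.25 | 0.013 | 5.1% |
| 5% | 0.5 | 0.025 | 5.3% |
| 15% | 0.5 | 0.075 | 8.0% |
| 28% | 0.5 | 0.14 | 14.7% |
| 28% | 1.0 | 0.28 | 43.7% |

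The last two rows put every loss in the VR arm, up to the most the cap allows if 172 are still to complete. With g = 0 there is no bias.

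**The case for a change.** The best case for the concern is that naming groups by randomization identifies the comparison but does not promise that everyone randomized is kept. The plan has no intention-to-treat statement and no missing-data rule, and the only text on who counts towards 172 is the completer phrase. An analyst could take either reading, and one sentence would settle it at no cost in participants.

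The silence is real, and that part stands. The rest is weaker. That the VR arm's condition is harder to meet is inferred from counting steps, since no completion rates are given, and the wellness forms are five items each. That an early stopper is dropped and replaced is not in the text and sits badly with section 8f. The sizeable error rates need three assumptions together: an exclusion rule that the plan lacks, exclusions confined to the VR arm, and a strong link between stopping at the baseline visit and anxiety measured later, on the procedure day. The weaker that link, the smaller g and the shift.

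**Conclusion.** The concern does not hold as a fault in the plan. A recruitment count in a feasibility paragraph does not define an analysis set, and the section that governs the analysis carries no completion condition. Followed as written, section 9b compares the randomized groups on the procedure-day STAI. That needs neither the wellness forms, nor a full VR session, nor the later survey, and it gives a sound result at the stated power: 90.3% with 86 per group, and up to 94.0% if all 200 have the outcome.

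What remains is missing detail: the analysis population and the handling of a missing procedure-day STAI are left implicit. The ordinary reading is to analyse every randomized participant who has the outcome in the assigned arm. The shifts of 0.013 to 0.28 SD tabulated above describe a different, completers-only analysis under assumed inputs, so they do not measure a defect in this plan. The conclusion rests on reading section 9b at face value. It would need revisiting only if participants with a procedure-day STAI were in fact left out.

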## **8. Study Design:**

### **a. Recruitment Methods**

Patients scheduled for outpatient LHC will be screened for inclusion/exclusion criteria via the catheterization laboratory schedule. Upon review of those medical records, patients who appear to meet all inclusion criteria and have no exclusion criteria and whose procedure date allows for a baseline visit preprocedure will be called by study personnel to discuss study participation. Whenever possible, a PDF of the consent form will be sent to the patient directly (e.g. via email or fax). If the immediate transmission of a consent form is not technologically possible, study personnel will verbally present all elements of the study. If the patient chooses to proceed with participation, a date and time will be agreed upon to meet at an agreed upon location (Spectrum Health facility whenever amenable). At that visit, study personnel will again review all elements of the consent form, procure written consent and then proceed with baseline activities. A one-time gift card valued at \$25.00 will be provided to the participant at the conclusion of the visit. The total number of participants to be enrolled in this study will be up to 200.

### **b. Inclusion and Exclusion Criteria**

#### *Inclusion Criteria*

- Scheduled to undergo a left-heart catheterization procedure at the Meijer Heart Center
- 18-75 years of age
- Signed study consent form

#### *Exclusion Criteria*

- History of cardiac procedure(s) in a cardiac catheterization laboratory
- History of seizures, migraine headaches or severe susceptibility to motion sickness
- Currently taking psychotropic drugs or on long-term psychotropic treatment
- Unable to read and speak English
- Visually impaired
- Unable to provide written consent

### **c. Study Endpoints**

The primary measure of interest in the present study is patient anxiety, as measured using the State Trait Anxiety Inventory (2, 3).

In all patients, anxiety will be assessed using this tool at baseline (prior to randomization) and again on the day of the procedure, just prior to undergoing catheterization.

The primary outcome of this study is the anxiety level measured just prior to catheterization, which will be compared in the two study groups.

The preparedness tool results will be compared between the two groups as a secondary analysis.

d. Procedures Involved in the Research

**Standard procedural education.** Standard procedural education for all patients undergoing cardiac catheterization at our site formally comes from two sources. First, it is provided verbally by clinical personnel, including physicians and nurses, during routine clinical interactions (i.e. at the time of office visits) and during subsequent phone calls made by the patient to clinical personnel requesting additional procedural information. Second, clinical personnel provide all patients with an information sheet that describes cardiac catheterization (attached as Appendix A; also available online at [www.kramesondemand.com](http://www.kramesondemand.com)).

**Virtual reality.** The VR experience developed for this study will be provided to participants by study personnel using a smartphone (Moto G, Motorola, Schaumburg, Illinois) and a viewer headset (View-Master, Mattel, Segundo, California). This interactive VR experience was filmed using a commercially available camera (360fly 4K, 360FLY, Pittsburgh, Pennsylvania) and developed using proprietary software by Carnevale Interactive (Grand Rapids, Michigan). The VR simulation will allow participants to experience aspects of their procedural day, starting with arrival in the lobby of the catheterization center. The simulation will progress to the catheterization laboratory registration and waiting room, followed by the pre-procedural holding area and finally the procedure room. In each location, the participant will be able to virtually explore the space and have the option of clicking on certain objects of interest, which will trigger an audio description of the object and its purpose.

**Visit 1 - Baseline.** All participants will be required to meet with study personnel at an offsite locale (Spectrum Health facility whenever possible) prior to the scheduled LHC to conduct the baseline visit. Once informed consent is obtained, study personnel will administer the State Trait Anxiety Inventory (STAI) assessment to all participants.

**Randomization.** Following the completion of the STAI assessment, participants will be randomized in a 1:1 fashion to undergo either VR combined with standard procedural education or to standard procedural education alone. Prior to enrollment of the first participant, Spectrum Health Office of Research Administration statisticians (who are not be study personnel) provided the randomization assignment schema to Cardiovascular Research staff (also not study personnel). Each assignment was placed in an envelope in the order designated by the statisticians' assignment schema. The envelopes were sealed and sequentially numbered from "1" to "200". The envelopes were stored in the research office in the high-density storage area.

Due to the COVID-19 Pandemic, study personnel are now working primarily from home.

In order to maintain the randomization schema as designed as well as reduce the need for staff to go into the hospital to collect randomization envelopes (thereby reducing their risk of exposure), the randomization process will be, for the remainder of the study, via REDCap database. The coordinator attending the enrollment visit will use REDCap to learn the randomization assignment for that participant while in the field, thus maintaining the blind.

For participants randomized to standard procedure education alone, the baseline visit will be complete. Participants will be thanked (and provided a gift card) and remaining study activities will be reviewed.

For participants randomized to VR intervention, the following will occur:

- A baseline wellness self-assessment will be administered (reporting on absence or presence and degree of severity of headache, nausea, dizziness, fatigue and vision abnormalities)
- The participant will be asked to confirm she or he is seated comfortably and study personnel will ensure the chair and participant are free of direct obstruction
- The participant will be shown the individual components of the VR system (View-Master with smartphone inserted; external speaker for audio projection; monitor for study staff to observe what the participant is experiencing), be given instructions on how to use the device and encouraged to ask questions.
- Once the participant indicates she or he is ready, they'll be asked to begin the VR experience. Study personnel will stay in the room with the participant for the entire duration and will be viewing on the monitor what the participant is experiencing virtually. Study personnel will provide guidance and answer questions regarding the technology and its use but will not answer questions regarding the facilities, prep, procedure or recovery (this will be explained prior to starting the VR experience).
- When the participant indicates she or he is finished with the VR experience and has had a few minutes to orient, the wellness self-assessment will be administered again.
- Participants will be thanked for their participation (and provided a gift card) and remaining study activities will be reviewed.

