## Appendix B – State-Trait Anxiety Inventory (STAI)

**SELF-EVALUATION QUESTIONNAIRE STAI Form Y-1**

Please provide the following information:

Name \_\_\_\_\_ Date \_\_\_\_\_ S \_\_\_\_\_  
Age \_\_\_\_\_ Gender (Circle) M F T \_\_\_\_\_

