**DIRECTIONS**

A number of statements which people have used to describe themselves are given below. Read each statement and then circle the appropriate number to the right of the statement to indicate how you generally feel.

	NEVER	SOMETIMES	ALMOST ALWAYS
21. I feel pleasant.....	1	2	3
22. I feel nervous and restless.....	1	2	3
23. I feel satisfied with myself.....	1	2	3
24. I wish I could be as happy as others seem to be.....	1	2	3
25. I feel like a failure.....	1	2	3
26. I feel rested.....	1	2	3
27. I am "calm, cool, and collected".....	1	2	3
28. I feel that difficulties are piling up so that I cannot overcome them.....	1	2	3
29. I worry too much over something that really doesn't matter.....	1	2	3
30. I am happy.....	1	2	3
31. I have disturbing thoughts.....	1	2	3
32. I lack self-confidence.....	1	2	3
33. I feel secure.....	1	2	3
34. I make decisions easily.....	1	2	3
35. I feel inadequate.....	1	2	3
36. I am content.....	1	2	3
37. Some unimportant thought runs through my mind and bothers me.....	1	2	3
38. I take disappointments so keenly that I can't put them out of my mind.....	1	2	3
39. I am a steady person.....	1	2	3
40. I get in a state of tension or turmoil as I think over my recent concerns and interests.....	1	2	3

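### Does the plan leave the primary anxiety score open by naming the State-Trait inventory without saying which of its two forms counts?

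*Combined protocol and SAP*

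**What the plan says.** Section 8c names the instrument: "The primary measure of interest in the present study is patient anxiety, as measured using the State Trait Anxiety Inventory". It then fixes the time point: "The primary outcome of this study is the anxiety level measured just prior to catheterization". The same tool is used at baseline, before randomization. Section 8d repeats only that the STAI is administered at both visits, and the list of data under Visit 2 is equally general: "The data collected for this study entails the State-Trait Anxiety Inventory results".

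Appendix B holds two questionnaires. The first is headed "SELF-EVALUATION QUESTIONNAIRE STAI Form Y-1"; its items 1 to 20 ask about feelings at the moment of answering. The second, Form Y-2, has items 21 to 40 and asks the respondent to "circle the appropriate number to the right of the statement to indicate how you generally feel".

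Section 9a sizes the trial on a two-sample t-test for the primary endpoint, "in order to detect an effect size of 0.5 between the groups at 90% power", with 86 patients per group. Section 9b compares anxiety levels between groups and adds a within-group test: "To determine if there is a difference in anxiety before and after the use of VR a paired t-test will be used". Outside Appendix B, no section names a form, a state score, a trait score or a scoring rule.

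**The concern.** A primary outcome should be identifiable from the plan. Here the instrument and the time are fixed but the score is not. Taken by itself, the sentence in Section 8c could be met by a Y-1 total, a Y-2 total or a sum of all 40 items, provided the form was completed at Visit 2. The effect size, the between-group test and the paired test all depend on that score, and the plan gives no standard deviation or point difference from which it could be inferred.

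The timing sharpens the worry. The randomization text in Section 8d shows the trial already in progress: "the randomization process will be, for the remainder of the study, via REDCap database". If both forms are being collected, more than one candidate score could be accumulating. Two things would then be at stake: the false-positive rate, if the score were chosen after the results were seen, and power, if the chosen score diluted the effect on present-moment anxiety.

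**Working it through.** **1. The plan's own figure.** Inputs from Section 9a: standardized difference d = 0.5, alpha 0.05, power 90%, two-sample t-test. Equal groups come from the 1:1 allocation in Section 8d. Sidedness is not stated, so two-sided is tried first.

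- Normal approximation: n per group = 2(1.960 + 1.282)² / 0.5² = 84.1, rounded up to 85.
- Exact noncentral t with n = 86: degrees of freedom 2 × 86 − 2 = 170, noncentrality 0.5 × √(86/2) = 3.28, power 0.903. This is the smallest n that reaches 90%.
- A one-sided test would need only 70.

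The stated 86 per group is therefore reproduced by the exact two-sided test. The arithmetic is sound.

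**2. Which score do the documents point to?** Each candidate can be set against what the plan says.

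| Feature of the plan | Form Y-1 | Form Y-2 | 40-item sum |
|---|---|---|---|
| Aim in Section 4: less anxiety before the procedure | fits | poor fit: asks about feelings in general | half the items do not address it |
| Section 5: anxiety in anticipation of the procedure | fits | poor fit | mixed |
| Section 8c: level immediately before catheterization | fits: asks about the present moment | timing has little meaning for a general disposition | mixed |
| Section 9b: paired test for change after VR | fits: a quantity that can move | weak fit | mixed |
| Any mention of adding the forms together | not needed | not needed | none |

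Only Y-1 fits throughout. The two forms also carry separate directions, and nothing in the plan suggests combining them.

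**3. Consequence under Y-1.** Section 9a attaches d = 0.5 to the primary endpoint. If that endpoint is the Y-1 score, then d = 0.5, 86 per group and 90.3% power all stand.

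**4. What would have to happen for harm to follow.** The plan gives no standard deviations, correlations or trait effect, so everything in this step rests on assumptions.

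*Summed score.* Suppose d = 0.5 holds for Y-1, VR has no effect on Y-2, and the 40 items are added. With k = trait SD / state SD and correlation r, d for the sum = 0.5 / √(1 + k² + 2rk). Power at 86 per group:

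| k | r = 0 | r = 1 |
|---|---|---|
| 1.0 | d = 0.354, power 63.5% | d = 0.250, power 37.1% |
| 0.8 | d = 0.390, power 72.1% | d = 0.278, power 44.1% |
| 0.5 | d = 0.447, power 83.0% | d = 0.333, power 58.5% |

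*Free choice between forms after seeing both.* The false-positive rate is 1 − P(|Z₁| < 1.96 and |Z₂| < 1.96), with Z₁ and Z₂ bivariate normal with correlation r. It is 9.3% at r = 0.4, 8.8% at r = 0.6 and 7.8% at r = 0.8, against a nominal 5%. In the favourable direction alone it is 4.7%, 4.4% and 3.9%, against 2.5%.

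These figures show that the choice of score would matter if it were really open. They do not show that it is: no section plans a sum, a test of both forms or a later choice.

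**The case for a change.** The strongest reply is that pre-specification exists so that readers need not infer. Form Y-2 is attached with no stated purpose or visit, the trial is recruiting, and one sentence would settle the matter at almost no cost. A reader cannot confirm from the text alone that a reported score was the planned one. Form Y-1 also mixes calm and tense statements on one scale, so even a Y-1 total needs a rule for reversing items, and none is written down.

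Much of this is true as description. The score is not named, and the scoring rule and the role of Y-2 are missing. The inference that a Visit 2 result from any form would serve equally well does not stand, because it reads one sentence of Section 8c apart from the aim, the timing and the tests. The effect size is not a separate gap either, since Section 9a already ties it to the primary endpoint. The missing reversal rule is a detail of the same kind: the direction of each Y-1 item is plain from its wording, and an analyst forming a total would align the items.

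**Conclusion.** The concern does not call for a change. Section 8c names an instrument rather than a score, but the plan as a whole leads a competent analyst to the Form Y-1 score at Visit 2. With that score, 86 per group gives 90.3% power at d = 0.5, and the tests, sample size and data collection are as planned. No stated rule or number is wrong. Naming the form would record the natural reading without altering the trial or its conclusion.

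This rests on two assumptions: that Y-1 is the score the team intended, which the aim and timing support but no sentence states, and that d = 0.5 was meant for it. The power range of 37% to 83% and the false-positive range of 7.8% to 9.3% are hypothetical and carry no weight here. A report that used Form Y-2 or a 40-item sum as the primary score would depart from the natural reading and would deserve a question then.
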